I. Study Design:

This will be a randomized controlled double blinded study.

Our study will include 100 patients having elective cesarean section at Cedars-Sinai Medical Center. Patients will be randomized in two groups: the first group will receive active warming with VitaHeat underbody heating mattress in preoperative holding area for 15 min, during the surgery and in PACU; second group will not receive active forced air or resistive mattress warming; both groups will receive the standard patient blankets and warmed intravenous fluids.

The observer and patient will be blinded as to the group assignment. Another anesthesiologist will perform the randomization table and turn the VitaHeat warming mattress on or off.

2. Study Device

VitaHeat will loan the underbody heating mattresses for the duration of the study.

3. Inclusion/Exclusion

Inclusion criteria:

- will be age >18 years,
- singleton pregnancy >37 weeks,
- neuraxial anesthesia,
- healthy afebrile patients.

Exclusion criteria:

- severe uncontrolled medical problems (e.g. uncontrolled diabetes),
- preeclampsia,
- pre-operative temperature >38degrees C,
- BMI>40kg/m2.
- Neonates of uncertain viability
- Nonviable neonates

4. Study Procedures

Patient temperature will be measured with Exergen temporal scanner TAT -5000 at the following events and intervals: in preoperative area, at time of neuraxial block (anesthesia) is placed, at delivery of the fetus, then every 15 min, at application of wound dressing, on arrival to recovery, then q 15 min until normothermia is achieved.

Shivering will be recorded and graded on the following scale as used in previous studies:

0 - no shivering,

1 - shivering not interfering with monitoring or causing distress,

2 - shivering interfering with OR patient monitoring devices (ECG, BP, Pulse oximeter) and causing patient distress.

During the temperature monitoring period we will record patient's vital signs as dictated by standard of care: heart rate, noninvasive blood pressure, pulse oximetry and episodes of interruption of monitoring secondary to a moving artifact. Other recorded variables will be room temperature, humidity, duration of surgery, estimated blood loss, hemoglobin level before surgery and on POD#1.

We will record time of skin-to-skin contact, initiation of breastfeeding, length of hospital stay, and incidence of surgical wound infection. Thermal comfort will be evaluated at the same time points as temperature, using a visual analog scale, in which 0 is the worst imaginable cold, 50 is temperature comfort, and 100 identifies the worst imaginable heat. We will ask the patients to provide a satisfaction score for the quality of care using a scale 0-100, 0=extremely unsatisfied, 100=extremely satisfied.

Neonatal parameters: rectal temperature at delivery and Apgar scores at 1 and 5 minutes will be recorded as routinely measured by the assigned nurse taking care of the neonate in the delivery room.

A review of medical records will be performed to determine the length of hospital stay and surgical wound infection rate.

For patients with no data for their postoperative course (outside of the Cedars-Sinai electronic medical record system) we will contact them via telephone to inquire about postoperative surgical wound infection complications. The call will take place 30 days after cesarean section was performed.

STATISTICS AND DATA HANDLING:

Using results from a previous published study, power analysis was performed to determine the sample size necessary to detect a temperature difference of 0.2 degree C with power 0.8, a type 1 error 0.05 and standard deviation 0.5 degree C. We calculated 50 patients in each group to detect such an effect.

Patients will be randomized in two groups: with or without active warming. A computer generated randomization number will be assigned to each patient, patients will not be aware of their group allocation.

Numeric variables: temperature, blood loss, transfusion rate, time to initiate skin to skin contact or breastfeeding, patient thermal comfort and satisfaction score and length of hospital stay will be compared with a unpaired Student t-test or Mann-Whitney U-test depending on data distribution. Categorical variables: incidence of perioperative hypothermia, shivering, wound infection rate, transfusion rate will be compared with chi-square test or Fisher's exact test.

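### Recovery temperature is read only until each patient is normothermic, so a comparison at a single post-arrival time would use outcome-selected patients and understate a constant warming effect

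*Combined protocol and SAP*

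**What the plan says.** Section 4 (Study Procedures) sets temperature readings from the preoperative area to wound dressing, and then "on arrival to recovery, then q 15 min until normothermia is achieved". No temperature defining normothermia is given.

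Section I (Study Design) has the mattress in use "in preoperative holding area for 15 min, during the surgery and in PACU", so the intervention continues while these readings are taken.

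The section on statistics and data handling lists temperature among the numeric variables that "will be compared with a unpaired Student t-test or Mann-Whitney U-test depending on data distribution". It names no time point, summary measure or longitudinal model, and gives no rule for readings that are absent because measurement has stopped. The sample size is set "to detect a temperature difference of 0.2 degree C with power 0.8, a type 1 error 0.05 and standard deviation 0.5 degree C", with no time point attached to the difference.

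Comfort follows the same schedule: "Thermal comfort will be evaluated at the same time points as temperature".

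**The concern.** The rule that ends measurement is the outcome itself. A patient who is normothermic on arrival has no 15-min temperature, and one who is normothermic at 15 min has no 30-min temperature. If warming works, more warmed than control patients leave the series early, and those who remain in the warmed arm are its coldest members. An unpaired test at 15 or 30 min would then compare two differently selected subsets, not the randomized groups.

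Post-arrival readings are the only post-arrival temperature data on the PACU part of the warming. The risk is a mistaken conclusion that warming in recovery does not raise temperature. Readings that were never taken cannot be recovered later.

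**Working it through.** **The plan's own figure.** For two groups, n per group = 2 × [SD × (1.96 + 0.842) / difference]² = 2 × [0.5 × 2.802 / 0.2]² ≈ 98.1, so 99, not 50. Without the factor 2 the result is 49.06, which rounds up to 50. With 50 per group, two-sided power is about 0.51 even when every patient is read. That is a separate error, but it sets the baseline here: only the drop below about 0.50 is due to selection.

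**Inputs.**
- From the statistics section: difference 0.2 °C, SD 0.5 °C, 50 per arm.
- Assumed, because the documents do not give them: threshold 36.0 or 36.5 °C; control arrival mean 35.5–36.0 °C (base case 35.8); between-patient SD 0.4 °C; rewarming 0–0.25 °C per 15 min, equal in both arms (base case 0.12); warming effect a constant shift. The thresholds only illustrate the arithmetic and are not proposals.
- The correlation between readings follows: ρ = 0.4² / 0.5² = 0.64.

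**Expected difference at 15 min.** A patient is read at 15 min only if her arrival reading is below the threshold c. For an arm with arrival mean μ, let z = (c − μ) / 0.5. The share still read is Φ(z). Their mean arrival temperature lies below μ by s = 0.5 × φ(z) / Φ(z). A fraction ρ of that shortfall carries over to the next reading, and equal rewarming cancels, so

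expected difference = 0.2 + ρ × (s_control − s_warmed).

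Base case:
- c = 36.0. Control: z = 0.4, share 0.655, 33 patients, s = 0.281. Warmed: z = 0, share 0.500, 25 patients, s = 0.399. Difference = 0.2 + 0.64 × (0.281 − 0.399) = 0.125 °C.
- c = 36.5. Control: z = 1.4, share 0.919, 46 patients, s = 0.081. Warmed: z = 1.0, share 0.841, 42 patients, s = 0.144. Difference = 0.2 + 0.64 × (0.081 − 0.144) = 0.16 °C.

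Arrival means of 35.5 and 36.0 °C give 0.145 and 0.113 °C at the 36.0 °C threshold, and 0.180 and 0.145 °C at 36.5 °C. The shortfall is always in the same direction, because cutting a normal distribution from above moves its mean by less than the shift in the underlying mean. It vanishes only if readings are uncorrelated.

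**Simulation of the base case** (50 per arm, each patient dropped after her first reading at or above the threshold, t-test on those still read):

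| Analysis | Power, 36.0 °C | Power, 36.5 °C |
|---|---|---|
| Arrival (all patients) | 0.51 | 0.51 |
| 15 min, patients still read | 0.18 | 0.35 |
| 30 min, patients still read (24 v 15; 42 v 36) | 0.11 | 0.26 |
| Per-patient average including arrival | 0.54 | 0.60 |
| Per-patient average excluding arrival | 0.21 | 0.44 |
| Log-rank, time to normothermia | 0.47 | 0.53 |
| Repeated-measures model, truncated 0/15/30 min | 0.57 | 0.61 |
| Fixed 0/15/30-min average, all patients | 0.62 | 0.63 |

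The repeated-measures row used a random intercept, a constant effect and known variance components; it recovered 0.20 °C at both thresholds.

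**Range over the assumptions.** At 30 min the expected difference is 0.09–0.13 °C (36.0 °C) and 0.12–0.17 °C (36.5 °C). Varying the between-patient SD over 0.3–0.474 °C widens the 15-min range over both thresholds to 0.08–0.19 °C, with power 0.09–0.47. With no true effect the two arms are selected alike, and simulated type I error at 15 and 30 min was 0.043–0.058.

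**The case against.** The strongest reply is that the plan never says it will test individual post-arrival times. It says only that temperature will be compared. If the comparison is made at arrival or earlier, nothing is lost; if it uses a per-patient average including arrival, most of the power survives, although the mean difference can shrink when patients rewarm. This stands, and it makes the point conditional. It does not remove it: the plan neither excludes such tests nor names an alternative, and comparing arms at each scheduled time is a natural use of this schedule.

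Reading until normothermia also has a legitimate purpose: it follows each patient to recovery and supports time to normothermia, resolved to 15 min. True, but that outcome is not in the analysis section.

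The size rests on undocumented inputs. That also stands. At 36.5 °C with a control arrival mean of 35.5 °C, about 49 v 47 patients are read and the expected difference is 0.18 °C, a small loss.

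A reader might infer three stronger things that the documents do not support:
- That every temperature comparison is biased. Readings through recovery arrival do not depend on the rule.
- That no usable recovery data remain. Shivering has no stated stop at normothermia, and satisfaction is also scored.
- That the rule could create a false positive. It does not inflate type I error.

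**Conclusion.** The point holds in conditional form. As written, the measurement rule and the open-ended test allow a comparison of outcome-selected subsets at a post-arrival time. For a constant shift with equal SDs and positively correlated readings, that comparison understates a true 0.2 °C effect: to about 0.11–0.15 °C at 15 min with a 36.0 °C threshold and 0.14–0.18 °C with 36.5 °C, under the stated assumptions. If the effect changes over time in recovery, the size, and possibly the direction, could differ.

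Thermal comfort shares the selection. Its bias depends on how closely comfort tracks temperature and is not quantified here.

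This should be corrected, with medium confidence in its practical size, because the threshold that drives the size is undefined.

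**What to change.** **Preferred.** Take recovery temperature and comfort readings at a fixed set of times in every patient, whatever her temperature (for example arrival, 15 and 30 min). Compare the arms at those times or by a prespecified average over them. The cost is a few non-invasive readings and comfort scores per patient. This must be settled before data collection.

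**If the schedule is kept.**
- Limit simple between-group tests of temperature and comfort to time points shared by all patients, that is, through recovery arrival.
- Analyse later temperatures with a likelihood-based repeated-measures model that includes the arrival reading. This is valid because stopping depends only on temperatures already recorded, so it requires that the stopping rule is followed and every reading is kept. It needs no extra measurements.
- Time to normothermia from arrival can be supplementary. State the threshold in advance, count patients normothermic on arrival as events at that reading, and acknowledge that censoring at the end of recovery observation may be informative. It removes the selection but adds little or no power over the arrival test.

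This alternative costs a few sentences of analysis wording and one model. Neither option repairs the sample size, which needs its own correction.

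### Drugs given for shivering are not recorded, so shivering suppressed by treatment cannot be told from shivering that never occurred

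*Combined protocol and SAP*

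**What the plan says.** Section 4, Study Procedures, sets up the outcome: "Shivering will be recorded and graded on the following scale as used in previous studies". The scale runs from 0 (none) through 1 (neither disturbing monitoring nor distressing) to 2 (both). The section STATISTICS AND DATA HANDLING then gives the analysis: "Categorical variables: incidence of perioperative hypothermia, shivering, wound infection rate, transfusion rate will be compared with chi-square test", with Fisher's exact test as the alternative.

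Section 4 also lists what else is collected. During temperature monitoring this is "heart rate, noninvasive blood pressure, pulse oximetry and episodes of interruption of monitoring secondary to a moving artifact". The remaining perioperative items are given as: "Other recorded variables will be room temperature, humidity, duration of surgery, estimated blood loss, hemoglobin level before surgery and on POD#1". Later outcomes follow: "We will record time of skin-to-skin contact, initiation of breastfeeding, length of hospital stay, and incidence of surgical wound infection". The chart review has a stated and narrow purpose: "A review of medical records will be performed to determine the length of hospital stay and surgical wound infection rate".

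No drug appears in any of these lists. The plan neither restricts nor standardizes drugs given for shivering, and it does not say how a treated patient is to be scored.

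**The concern.** Treatment for shivering is prompted by the outcome being measured. A patient treated before a grading can be scored 0. A patient treated at grade 1 may never reach grade 2. If warming works, more unwarmed patients shiver, so more of them are candidates for treatment. Any suppression then falls more heavily on the unwarmed arm and narrows the observed contrast. Because it arises after randomization and as a consequence of it, randomization does not balance it.

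Blinding does not remove it either. Section I states that "The observer and patient will be blinded as to the group assignment", but treatment can follow the patient's visible state without anyone knowing the allocation.

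What is at stake is interpretation. With no drug record, a small or null difference in shivering could reflect an ineffective mattress or more treatment in the unwarmed arm, and the collected data could not separate the two.

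**Working it through.** **1. Is the drug information captured anywhere?**

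| Place in the plan | What is collected | Drugs for shivering? |
|---|---|---|
| Section 4, vital signs | Heart rate, blood pressure, oximetry, monitoring interruptions from movement | No |
| Section 4, other variables | Room conditions, surgery duration, blood loss, hemoglobin | No |
| Section 4, later outcomes and neonatal data | Skin-to-skin, breastfeeding, stay, wound infection, comfort, satisfaction, neonatal temperature, Apgar | No |
| Section 4, chart review | Length of stay, wound infection | No |

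The movement-artifact item captures disruptive shivering, not its treatment.

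**2. Which sequences change which result?**

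| Sequence | Any-shivering incidence | Grade reached |
|---|---|---|
| Onset graded, then treated | Unchanged | Grade 2 may be averted |
| Treated before a grading, because of the patient's state | Can become 0 | Can become 0 |
| Routine prophylaxis regardless of state | Lowered in both arms; use balanced by randomization | Same |

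Section 4 gives measurement times for temperature and ties thermal comfort to them. It gives none for shivering, so the frequency of the second sequence cannot be judged.

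**3. How large could the effect be?**

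The plan has no shivering rate or power figure to reproduce. The only input taken from it is 50 per arm, from the statistics section. That figure was derived for temperature, and whether it follows from its own inputs is a separate matter. The true rates and hidden shares below are assumptions.

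Observed rate = true rate × (1 − share of would-be shiverers hidden by a drug).

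Power is exact. For every pair of counts (x, y) from 0 to 50, compute χ² = 100(x − y)² / [(x + y)(100 − x − y)]. Then add the product of the two binomial probabilities wherever χ² exceeds 3.84 (two-sided 0.05, no continuity correction).

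True rates 50% unwarmed and 30% warmed:

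| Hidden, unwarmed / warmed | Observed rates | Difference | Ratio | Power |
|---|---|---|---|---|
| 0 / 0 | 50% / 30% | 20 points | 0.60 | 0.55 |
| 10% / 3% | 50 × 0.90 = 45% / 30 × 0.97 = 29.1% | 15.9 points | 0.65 | 0.38 |
| 25% / 10% | 50 × 0.75 = 37.5% / 30 × 0.90 = 27% | 10.5 points | 0.72 | 0.20 |

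A second set of assumed rates, 40% and 15%, uses the pooled normal approximation, power = Φ{[d − 1.96·√(2p̄(1 − p̄)/50)] / √[(p₁(1 − p₁) + p₂(1 − p₂))/50]}:

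| Hidden, unwarmed / warmed | Observed rates | Difference | Ratio | Power |
|---|---|---|---|---|
| 0 / 0 | 40% / 15% | 25 points | 0.375 | 0.81 |
| 25% / 25% | 30% / 11.25% | 18.75 points | 0.375 | 0.64 |
| 25% / 10% | 30% / 13.5% | 16.5 points | 0.45 | 0.52 |
| 40% / 10% | 24% / 13.5% | 10.5 points | 0.56 | 0.27 |

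Equal hidden shares shrink the difference but leave the ratio alone. The ratio moves toward 1 only when the hidden share is larger in the unwarmed arm.

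**The case against.** The strongest reply is that the planned comparison is largely protected. The statistics section names incidence, and treatment to stop shivering follows onset. If onset is graded first, the event is already counted. This stands, and it confines the bias in incidence to treatment given before a grading.

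Second, prophylaxis is not triggered by shivering, and routine use is balanced by randomization. This also stands. Only drugs given early because a patient looks cold or is starting to shiver would differ by arm, and the documents do not describe such practice.

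Third, a reader might infer that a planned severity comparison is compromised, for instance one in which grade 2 occurs in 20% and 8% and early treatment halves both. The chi-square power would drop from 0.43 to 0.20. The documents do not support that reading. No grade-2 or worst-grade test is clearly planned. Halving both arms leaves the ratio at 0.4, so it is not arm-dependent masking. At 10% and 4% the expected count is (5 + 2)/2 = 3.5 per arm, where the plan's Fisher option would ordinarily apply; using it whenever expected counts fall below 5 gives power 0.12, not 0.20.

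Fourth, at assumed rates of 50% and 30% the power is only 0.55 with no drugs at all, so a null shivering result would be weak evidence anyway. That is true, but low power and a shift toward no effect are different faults, and only the second can be examined by recording the drug.

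Finally, the information could probably be recovered later from the clinical record. That supports a low cost, but the plan's chart review does not now cover it, and a counting rule chosen after the data are seen is weaker than one fixed beforehand.

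**Conclusion.** The omission is real, and its consequence is conditional. If drugs are given for shivering, if some are given before a grading in response to the patient's state, and if warming works, the incidence comparison moves toward no effect and nothing in the collected data would reveal it. With no such drug use, or with onset always graded first, incidence is not biased.

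The documents give no shivering rate, drug use or hidden share, so the power falls shown (0.55 to 0.38 or 0.20; 0.81 to 0.52 or 0.27) illustrate a range under assumptions and are not estimates for this trial. A reader might infer that the planned shivering result is invalid or that any treatment biases it; the text supports neither. The trial was sized on temperature, and this point does not touch that comparison. It is a cheap improvement to a secondary comparison.

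**What to change.** Add one item to the recorded variables in section 4: any drug given for shivering, with agent, time, and whether it was given to prevent or to treat it, taken from the anesthesia and PACU record.

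Add to the statistics section that, in the incidence comparison, a patient treated for shivering counts as having shivered, while prophylaxis alone does not count as an event. Report the raw 0 to 2 grades unchanged, without a separate rank for treated patients, and tabulate treatment and prophylaxis by arm.

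The cost is one field from an existing record and a short addition to the analysis text. The small downside is that the combined endpoint includes a clinician's decision to treat, so observed shivering alone should be shown beside it. The change concerns recording and analysis only and sets no treatment rule.

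### Thermal comfort is best at 50 and worst at both ends of its scale, yet it goes untransformed into a t-test or Mann-Whitney test, which compares warmth rather than comfort

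*Combined protocol and SAP*

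**What the plan says.** Section 4, Study Procedures, defines the thermal comfort scale: "0 is the worst imaginable cold, 50 is temperature comfort, and 100 identifies the worst imaginable heat". The score is taken repeatedly: "Thermal comfort will be evaluated at the same time points as temperature, using a visual analog scale". In recovery, that schedule is "on arrival to recovery, then q 15 min until normothermia is achieved". The satisfaction score in the same section runs in one direction: "0=extremely unsatisfied, 100=extremely satisfied".

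The section Statistics and Data Handling puts both scores in one list of numeric variables: "thermal comfort and satisfaction score and length of hospital stay will be compared with a unpaired Student t-test or Mann-Whitney U-test", with the choice between the two tests depending on the data distribution. Neither section gives a transformation, a distance from 50, a comfort band, a rule for reading the direction of a difference, or a time point or per-patient summary for the comparison.

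**The concern.** Both planned tests respond to shifts up or down the scale. For satisfaction, up means better. For thermal comfort, up means warmer, which is better below 50 and worse above it. The intervention is "active warming with VitaHeat underbody heating mattress in preoperative holding area for 15 min, during the surgery and in PACU", so a shift towards the hot end is what one would expect. A significant upward shift could be reported as better comfort when the test has shown only that warmed patients feel warmer. If an arm mixes cold and hot patients, even a mean close to 50 can hide unchanged discomfort.

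A secondary gap is that the number of scores varies by patient, because the recovery series ends at normothermia, and the plan does not say which score or summary enters the test.

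**Working it through.** **Inputs.** The documents give the scale, the tests and 50 patients per arm. They give no mean or SD for thermal comfort, so every mean below is an assumption and each result is shown for SD 10 / 15 / 20. One score per patient is assumed. The plan has no figure of its own on this point. Its 50 per group was calculated for temperature and serves here only as the arm size; whether it is right is a separate matter.

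**Discomfort measure.** Let D = |VAS − 50|. For a normal score with mean m and SD s, and d = |m − 50|:

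E(D) = s·√(2/π)·exp(−d²/2s²) + d·[1 − 2Φ(−d/s)]

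For example, with m = 40 and s = 15: 15 × 0.798 × exp(−100/450) + 10 × (1 − 2 × 0.2525) = 9.58 + 4.95 = 14.53. By symmetry m = 60 gives the same value. The results are:

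- m = 40 or 60: 11.67 / 14.53 / 17.91
- m = 45 or 55: 8.96 / 12.63 / 16.45
- m = 50: 7.98 / 11.97 / 15.96

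These ignore the scale limits. Clipping to 0–100 lowers the SD 20 values for m = 40 and m = 50 to about 17.7 and 15.9, which changes no conclusion.

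**Rejection rates.** Simulation of 20,000 trials, scores clipped to 0–100, two-sided 0.05:

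| Control vs warmed mean | Raw t-test rejects (%) | Mann-Whitney on D rejects (%) |
|---|---|---|
| 40 vs 50, cold relieved | 99.9 / 91.1 / 70.3 | 65.9 / 20.2 / 10.0 |
| 45 vs 55, equal discomfort | 99.9 / 90.9 / 69.9 | 4.6 / 4.9 / 4.9 |
| 45 vs 60, warmed arm worse | 100 / 99.9 / 95.8 | 39.8 / 13.1 / 7.7 |
| 40 vs half at 40, half at 60 | 98.2 / 84.9 / 65.5 | 4.5 / 4.9 / 4.7 |
| 30 vs 45, both arms cold | 100 / 99.9 / 95.9 | 100 / 94.3 / 58.9 |

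Hand check of 40 vs 50 at SD 15: the standard error is 15 × √(2/50) = 3, and Φ(10/3 − 1.96) = Φ(1.37) = 0.915, close to the simulated 0.911.

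**Reading the table.**

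1. The raw test rejects almost equally often for a true gain (40 vs 50) and for no change in discomfort (45 vs 55). A separate run at SD 12 gave 98.6% both for 40 vs 50 and for 50 vs 60, which are opposite in meaning.
2. When each arm lies on one side of 50, the arm mean helps. For 45 vs 60 the warmed mean exceeds 50 in about 100% of trials at all three SDs.
3. In the mixed arm it does not help. D has the same distribution in both arms, yet the warmed mean is within 5 points of 50 in 98.9% / 95.1% / 89.4% of trials. The proportion below 50 falls from 84% / 75% / 69% to 50%, exactly as in the true gain of 40 vs 50. Mean D stays at 11.7 / 14.5 / 17.9 in the mixed case and falls to 8.0 / 12.0 / 16.0 in the true gain.
4. When both arms are on the cold side, the raw and folded tests mostly agree.

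**The case against.** The strongest reply is that ordinary reporting would not mislead. No p-value by itself carries clinical meaning, the plan prints the anchors and nowhere says that higher is better, and a mean read against 50 exposes overheating in one-sided arms. The plan follows hypothermia, shivering and return to normothermia, so cold-side scores, for which the raw test ranks comfort correctly, are at least as plausible as a half-and-half mixture. All of this stands. It limits the importance of the point, but reading against 50 is not prespecified and the documents do not show on which side the scores will lie.

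A second reply is that the SD would give the mixture away. In the mixed arm it rises to about 14.1 / 17.9 / 21.9, against 10.0 / 14.9 / 19.5 in control, and a variance-ratio test rejects in 68% / 24% / 11%. That is a fair warning sign, about as strong as the folded test is for the true gain. It does not make the raw test a test of comfort, and the plan does not say which summaries will be reported.

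Third, D has low power, weights cold and heat equally without support in the documents, and adds a test to a long list with no multiplicity control. This also stands, and it is why D belongs beside the raw score and not in its place.

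Finally, the missing time point has nothing to do with the midpoint scale and affects temperature equally. That is correct; it is secondary here and adds no weight.

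**Conclusion.** The concern holds, as a minor point. The planned comparison measures thermal sensation, and its p-value alone does not separate relief of cold from overheating. How much this matters depends on where the scores fall, which the documents do not say: it is negligible if nearly all scores are below 50, largely visible from the arm means if each arm lies on one side of 50, and hidden from the means if an arm mixes cold and hot patients. The rejection rates rest on assumed means and SDs, roughly normal scores and one score per patient. They illustrate the problem and do not predict this trial's results. Thermal comfort is one of many listed outcomes, the sample size is built on temperature, and the raw data remain usable.

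**What to change.** Before unblinding, state the following in Statistics and Data Handling:

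- Keep the raw comparison, label it thermal sensation, and show each arm's mean or median against 50.
- Beside it, prespecify |VAS − 50| as a measure of discomfort, compared by Mann-Whitney and reported with the difference and its 95% confidence interval.
- Report by arm the proportions below and above 50. They show whether scores lie on one side, in which case the raw comparison can be read as comfort; they do not by themselves identify a mixed arm.
- Use one named time point, or one per-patient summary, for all of these.
- State that a non-significant |VAS − 50| result is not evidence of equal comfort, and that the measure treats equal distances on the cold and hot sides as equally uncomfortable.

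The cost is a few sentences and one derived variable, with no new data. The price is low power: at SD 10 / 15 / 20, about 66% / 20% / 10% for 40 vs 50 and 40% / 13% / 8% for 45 vs 60. The 95% interval for the difference in mean |VAS − 50| is about ±3 / ±4 / ±5 points, while the true gain of 40 vs 50 is only 3.7 / 2.6 / 2.0 points (11.67 − 7.98, 14.53 − 11.97, 17.91 − 15.96). It should therefore not be the only comfort result.

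### The stated inputs need about 100 patients per group, not 50; as planned, power for 0.2 °C is about 51%, not 80%

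*Combined protocol and SAP*

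**What the plan says.** The section STATISTICS AND DATA HANDLING reports a power analysis, based on a published study, to "detect a temperature difference of 0.2 degree C with power 0.8, a type 1 error 0.05 and standard deviation 0.5 degree C". Its conclusion is "We calculated 50 patients in each group to detect such an effect". The section I. Study Design agrees on the total: "Our study will include 100 patients having elective cesarean section", randomized in two groups.

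The same statistics section names the analysis. Numeric variables, with temperature listed first, are compared between groups by an unpaired Student t-test or, depending on the distribution, a Mann-Whitney U-test. The plan does not state whether the test is one- or two-sided, or which temperature reading (or summary of readings) the 0.2 °C and 0.5 °C refer to. It gives no allowance for dropout, and it specifies no baseline-adjusted, change-score or repeated-measures analysis.

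**The concern.** The printed difference and standard deviation give a standardized difference of 0.2 / 0.5 = 0.4. Fifty per group is about half of what two independent groups need at that effect size for 80% power.

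This is the plan's only justification of its size, and temperature is the only variable for which power is claimed. If the true effect is the planned 0.2 °C, the chance of missing it is about 49%, not the 20% that the plan implies. A reader who trusts the 80% figure could then take a null result as evidence that warming does not work, when the trial had only an even chance of showing the effect it was planned for.

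**Working it through.** **Inputs.** All are from STATISTICS AND DATA HANDLING unless noted.

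- Difference δ = 0.2 °C; standard deviation σ = 0.5 °C; power 0.80; α = 0.05.
- Stated size: 50 per group, allocation 1:1. The total of 100 is in I. Study Design.
- Test: unpaired, two groups. Two-sided testing is an assumption, because the plan does not say; the one-sided case is shown as well.

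**Can the stated 50 be reproduced?** Not with the two-group formula:

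n per group = 2 × (z₀.₉₇₅ + z₀.₈₀)² × (σ/δ)² = 2 × (1.960 + 0.842)² × (0.5/0.2)² = 2 × 7.849 × 6.25 = 98.1

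This rounds up to 99. The exact (noncentral t) calculation gives 99.08, so 100 per group. The total is 198 to 200.

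The only simple formula tried that comes close to 50 is the one for a single sample or for paired data, which lacks the factor of 2:

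n = 7.849 × 6.25 = 49.1 (normal), or 51.0 (t)

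The normal version rounds up to 50. That formula does not fit separate randomized groups compared by an unpaired test.

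**Power with 50 per group.** By the normal approximation, the standardized test statistic has mean 0.4 × √(50/2) = 2.00.

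| Test | n per group needed (normal / t, rounded up) | Power at 50 per group (normal / t) |
|---|---|---|
| Two-sided 0.05 | 99 / 100 | 0.516 / 0.508 |
| One-sided 0.05 | 78 / 78 | 0.639 / 0.634 |

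As a check, 100 per group gives two-sided power of 0.807 (normal) or 0.804 (t).

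**What 50 per group does support (two-sided, 80% power).**

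- With σ = 0.5 °C, the detectable difference is 2.802 × 0.5 × √(2/50) = 0.280 °C (normal), or 0.283 °C (t).
- With δ = 0.2 °C, the required standard deviation is 0.2 / (2.802 × √(2/50)) = 0.357 °C (normal), or 0.353 °C (t), against the stated 0.5 °C.

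**Mann-Whitney instead of the t-test.** On normal data its relative efficiency is 0.955, so the requirement rises slightly: 99.08 / 0.955 = 103.7, or 104 per group.

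**The case against.** The strongest defence is that the plan leaves some inputs open, and that a more efficient analysis could make 50 per group adequate.

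- *One-sided test.* Sidedness is not stated, so this reading is possible. It still needs 78 per group.
- *Baseline adjustment.* Taking 0.5 °C as the standard deviation of one reading, adjustment for preoperative temperature multiplies the requirement by 1 − ρ². To bring 98.1 down to 50 needs ρ = √(1 − 50/98.1) = 0.70. A change score needs 98.1 × 2(1 − ρ) = 50, so ρ = 0.75. The plan specifies neither analysis and gives no correlation. If 0.5 °C is already the standard deviation of a change, the requirement remains 99 to 100 per group.
- *Repeated readings.* Temperature is measured many times. As an illustration, averaging four readings with an assumed within-patient correlation of 0.3 multiplies the variance by (1 + 3 × 0.3)/4 = 0.475, which gives about 47 per group. At a correlation of 0.5 the factor is 0.625, which gives about 61. The plan does not describe such a summary, so this cannot support the printed figure.
- *Misprint.* An input could be wrong instead of the result: a standard deviation near 0.35 °C, or a difference near 0.28 °C, would fit 50 per group. The 50 itself is not a stray figure, because it agrees with the total of 100.

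Two points stand. The 51% applies to a two-sided, unadjusted comparison at a single time point, and should be labelled so. The cause of the error cannot be shown from the document. A dropped factor of 2, a per-group figure of 100 read as the total, and a misprinted input are all possible. Neither point makes the printed inputs and the printed sample size agree.

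**Conclusion.** The concern holds. The plan's own inputs require 99 to 100 patients per group, about twice the 50 stated. Power for 0.2 °C at 50 per group is about 51%, against a stated 80%.

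These figures assume a two-sided test of two independent groups with a standard deviation of 0.5 °C, no covariate adjustment and no losses. Under a one-sided test the shortfall is smaller (about 63% power) but remains. Losses would lower power further: with 45 evaluable patients per group, for illustration, it is about 47%. The error lies in the sole justification of the trial's size and can be verified from the document alone, so it must be corrected.

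**What to change.** The sponsor should first check the power calculation against its source to find which printed figure is wrong. If the inputs are as intended and the trial stays at 100 patients, remove the claim of 80% power for 0.2 °C and replace it with one of these statements:

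- 50 per group gives about 51% power (two-sided α = 0.05, unpaired t-test) for a difference of 0.2 °C with a standard deviation of 0.5 °C; or
- 50 per group gives 80% power for a difference of about 0.28 °C with the same standard deviation. This version should say why 0.28 °C is a difference worth detecting, since otherwise the effect has simply been fitted to the sample.

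Either statement should name the sidedness and the temperature reading to which it applies.

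If the sponsor prefers an analysis adjusted for preoperative temperature, power should be restated on the residual standard deviation. Reaching 80% for 0.2 °C then needs a baseline-outcome correlation of about 0.7, which has to be justified. The plan should also make clear that the baseline reading precedes the 15 minutes of preoperative warming, which it does not say at present.

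The cost is one reworded paragraph and a less favourable power or detectable difference; no extra patients are needed. Keeping 80% power for 0.2 °C with the unadjusted test would instead take about 200 patients, twice the planned enrolment.
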